**Schedule of Assessments**

Study Procedures	Screening Day -28 to Day -2	Day -1	Treatment Period		Follow-up (28-30 days postdose)
			Days 1 to 6		
Immunogenicity:					
Blood sampling d			Day 1 predose, Day 2 (24 h), Day 5 (96 h)		X
Safety and tolerability:					
Adverse event recording	X	X	Ongoing		X
Prior/concomitant medication monitoring	X	X	Ongoing		X
Clinical laboratory evaluations (including coagulation) d	X e	X e	Day 2 (24 h), Day 3 (48 h), Day 4 (72 h), Day 5 (96 h), and Day 6 (120 h e )		X
Supine blood pressure, supine pulse rate, respiratory rate and oral body temperature d	X	X	Day 1 predose, 2 h, 4 h, 12 h, Day 2 (24 h), Day 3 (48 h), Day 4 (72 h), Day 5 (96 h), and Day 6 (120 h)		X
12-lead ECG d	X		Day 1 predose, 2 h, 4 h, 12 h, Day 2 (24 h), Day 3 (48 h), Day 4 (72 h), Day 5 (96 h), and Day 6 (120 h)		X
Continuous 12-lead ECG			X f		
Physical examination d	X g		Day 1 predose, Day 2 (24 h), Day 3 (48 h), Day 4 (72 h), Day 5 (96 h), and Day 6 (120 h) h		X h

Abbreviations: ECG = electrocardiogram, h = hour; HIV = human immunodeficiency virus; min = minute.

a Interim medical history.

b In all females.

c Height measured at Screening only.

d Times (h) relative to dosing.

e Clinical laboratory tests to include lipid panel (fasted).

f Monitor for 12-lead ECG recording will be worn from 2 hours predose to 25 hours postdose on Day 1. Extraction timepoints will be 60, 45, and 30 minutes predose and at 0.25 hours, 0.5 hours, 1 hour, 2 hours, 4 hours, 6 hours, 8 hours, 10 hours, 12 hours, 24 hours postdose. Continuous 12-lead ECG will be performed on Groups A3 and A4 only.

g Performed between the Screening Visit and predose assessments.

h Symptom-directed physical examination at all timepoints other than Screening.

iPK urine sampling for males only

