## 1.4. Summary of Toxicology

### 1.4.1. Toxicology in Rats

A study was conducted to evaluate toxicity after a single dose of CPT31 when administered via SC injection to male Sprague-Dawley rats at 0, 10, 30, 60, and 100 mg/kg.

All animals survived to scheduled sacrifice at 24 hours postdose. In the 100 mg/kg dose group, 1/3 animals appeared slow and sensitive to touch at 8 hours postdose, and 3/3 animals were slightly lethargic with increased respiration rates at 24 hours postdose. All CPT31-treated animals had mild to moderate ISRs. No other adverse clinical or necropsy findings were observed. Based on these results, the maximum tolerated dose (MTD) of CPT31 in male Sprague-Dawley rats following single-dose SC administration is 100 mg/kg.

A Good Laboratory Practice (GLP)-compliant 14-day repeat-dose toxicity study evaluated the toxicity (including respiratory and CNS safety pharmacology endpoints) as well as the toxicokinetics (TK) of CPT31 in male and female Sprague-Dawley rats at dose levels of 0, 10, 20, or 60/40 mg/kg/day, administered daily via SC injection. The dose solution strength for all groups was 15 mg/mL. The 60 mg/kg/day dose was not tolerated, and several animals were found dead or were sacrificed moribund on Days 4-8. Dosing in this group was suspended on Day 4 and resumed on Day 7 at the reduced dose of 40 mg/kg/day in surviving animals (although these animals were inadvertently not dosed on Day 10 due to a protocol deviation). All animals that survived past Day 8 survived until their scheduled sacrifice on Day 15.

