## **1.7. Benefit-risk Assessment**

Subjects in this study will not gain any clinical benefits. Study subjects and others may benefit in the future from information learned from this study. Specifically, information learned in this study may lead to the development of safe and effective interventions to treat and/or prevent HIV transmission.

The risks of participation are primarily those associated with adverse reactions to the investigational medicinal product (IMP), although there may also be some discomfort from collection of blood samples and other study procedures.

Phlebotomy may lead to discomfort, feelings of dizziness or faintness, and/or bruising, swelling and/or infection. Good venipuncture practices reduce the pain and likelihood of bruising and secondary infection. Precautions will be taken with subjects who have a history of fainting or other vasovagal events during blood draws, including having the subject lie down during the procedure.

Subcutaneous injections can cause injection site swelling, warmth, and discomfort. These ISRs generally resolve within 3 days. Inadvertent administration of study product into a vein or into a nerve can occur. Injections are only administered by trained designated study personnel, and numerous precautions are taken to minimize this risk.

Electrocardiograms (ECGs) have no major risks. However, mild pain may be associated with removal of the electrodes and mild skin irritation may develop at the sites of electrode attachment.

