## **2. OBJECTIVES AND ENDPOINTS**

### **2.1. Objectives**

The primary objective of the study is:

- to assess the safety and tolerability of a single SC dose of CPT31 in healthy subjects

The secondary objectives of the study are:

- to characterize the single SC dose PK of CPT31
- to identify and characterize antibodies to CPT31

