## 5.2. Study Treatment Administration

All IMP vials will be removed from storage at 2°C to 8°C for between 5 to 60 minutes prior to dose preparation. The IMP vials will be swirled for approximately 3-5 seconds, IMP will be drawn up into 1 or more BD tuberculin syringes (0.3 or 1.0 mL), and syringes containing IMP will be used within 6 hours after dose preparation. Each dose of CPT31 and placebo will be administered by SC injection into the abdomen while the subject is in a semi-supine or sitting position. Subjects will be fasted for at least 8 hours prior to dosing and for at least 2 hours after dosing; a meal will be provided after the 2-hour postdose assessments are completed.

Subjects will be administered the IMP while semi-supine or seated and will remain semi-supine or seated for at least 30 minutes after dosing, except as necessitated by the occurrence of an AE(s) and/or study procedures.

The doses and estimated injection volumes are detailed in [Table 4](#). Rounding may be used based on measurable volumes in the appropriate syringe.

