## **7.3. Safety and Tolerability Assessments**

### **7.3.1. Adverse Events**

Adverse event definitions, assignment of severity and causality, and procedures for reporting SAEs are detailed in [Appendix 1](#).

The condition of each subject will be monitored from the time of signing the ICF to final discharge from the study. Subjects will be observed for any signs or symptoms and asked about their condition by open questioning, such as “How have you been feeling since you were last asked?”, at least once each day while resident at the study site and at each study visit. Subjects will also be encouraged to spontaneously report AEs occurring at any other time during the study.

All nonserious AEs, whether reported by the subject voluntarily or upon questioning, or noted on physical examination, will be recorded from initiation of study drug until study completion. Serious AEs will be recorded from the time the subject signs the ICF until study completion. The nature, time of onset, duration, and severity will be documented, together with an Investigator’s (or designee’s) opinion of the relationship to study drug. Photos may be taken of visible side effects, such as a skin rash, for the study records.

Adverse events recorded during the course of the study will be followed up, where possible, until resolution or until the unresolved AEs are judged by the Investigator (or designee) to have stabilized. This will be completed at the Investigator’s (or designee’s) discretion.

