### **7.3.5. Physical Examination**

A full physical examination or symptom-directed physical examination will be performed at the timepoints specified in the Schedule of Assessments in [Appendix 6](#).

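### After dosing, no scheduled assessment requires anyone to look at the injection site, so visible but symptomless local reactions can be missed and their incidence under-counted

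*Protocol*

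**What the plan says.** The primary objective in Protocol Section 2.1 is "to assess the safety and tolerability of a single SC dose of CPT31 in healthy subjects". Section 2.2.1 lists physical examinations and the incidence and severity of adverse events among the primary safety endpoints. Under Section 5.2, "Each dose of CPT31 and placebo will be administered by SC injection into the abdomen".

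Section 7.3.5 leaves the kind and timing of examination to the schedule: "A full physical examination or symptom-directed physical examination will be performed at the timepoints specified in the Schedule of Assessments". In Appendix 6 the Screening examination carries the footnote "Performed between the Screening Visit and predose assessments", and the footnote for the remaining examinations reads "Symptom-directed physical examination at all timepoints other than Screening". Those remaining examinations are at Day 1 predose, Days 2 to 6 and Follow-up.

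Section 7.3.1 describes how adverse events are found. At least once a day in residence, and at each visit, subjects are observed for signs as well as symptoms and "asked about their condition by open questioning". Anything noted on physical examination is also recorded, and visible side effects may be photographed.

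On the expected reactions, Section 1.7 names swelling, warmth and discomfort at the site and adds "These ISRs generally resolve within 3 days". Of the single-dose rat study, Section 1.4.1 says "All CPT31-treated animals had mild to moderate ISRs".

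SAP 8.6.1 tabulates treatment-emergent adverse events by preferred term and by severity. SAP 8.6.5 only lists safety and tolerability assessments not covered elsewhere. Neither document names an injection-site assessment.

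**The concern.** Swelling, redness, induration and nodules can be seen or felt by an examiner while giving the subject nothing to complain of. A symptom-directed examination does not go looking for such findings, and an open question may not bring them out. The remaining route is general observation by staff, which is unstructured. A subject can be observed for signs every day without the abdomen being uncovered.

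At stake is the completeness of one component of the primary objective in a first-in-human study of an injected product. A report of few local reactions could mean that there were few, or that few were noticed. The data as planned would not separate the two, because a site that was inspected and found clear looks the same in the database as a site that nobody inspected.

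**Working it through.** The plan gives no figure to reproduce here. The check is a reading of the schedule, followed by an illustration.

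**Step 1. What is scheduled after dosing (Protocol Appendix 6).**
- Physical examinations: Days 2, 3, 4, 5, 6 and Follow-up, which is 6, all symptom-directed.
- Full physical examinations: 0.
- Injection-site inspections or local tolerability scores: 0.
- Timepoints with vital signs, so with staff at a supine subject: 2, 4 and 12 h, Days 2 to 6 and Follow-up, which is 3 + 5 + 1 = 9.

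Protocol Section 7.3 and SAP 8.6 add no site assessment. Staff are already present often enough; what is missing is an instruction to look.

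**Step 2. Whether there is reason to look (Protocol Sections 1.2, 1.4 and 1.7).** Six subcutaneous toxicology studies are summarized:

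| Study | Injection-site finding reported |
|---|---|
| Rat, single dose | Yes, in all treated animals |
| Rat, 14-day GLP | None mentioned |
| Rat, 28-day GLP | Yes, at every active dose |
| Monkey, escalating doses | None described as an injection-site reaction |
| Monkey, 14-day, 10 to 80 mg/kg/day | Yes |
| Monkey, 14-day GLP | Yes |

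That is 4 of 6. On the other side, the rhesus maintenance study in Section 1.2 saw no injection-site reactions at 3 mg/kg/day. It is a pharmacology study outside the six, and its route is not stated.

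**Step 3. What incomplete detection does to a group of six.** Let p be the true proportion of active subjects with a visible site reaction and d the share of those reactions that is recorded. The documents give neither, so both are assumptions. The expected number recorded is 6 × p × d. The chance of recording at least one is 1 − (1 − p × d)^6.

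Worked case, p = 0.3 and d = 0.5: p × d = 0.15; expected number 6 × 0.15 = 0.9, against 6 × 0.3 = 1.8 with full detection; chance of at least one 1 − 0.85^6 = 0.623, against 1 − 0.70^6 = 0.882.

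Chance of recording at least one reaction among 6:

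| p | d = 1.0 | d = 0.75 | d = 0.5 | d = 0.25 |
|---|---|---|---|---|
| 0.1 | 0.469 | 0.374 | 0.265 | 0.141 |
| 0.3 | 0.882 | 0.783 | 0.623 | 0.374 |
| 0.5 | 0.984 | 0.940 | 0.822 | 0.551 |

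The column d = 1.0 is the best case for a scheduled inspection. The table shows how sensitive the recorded result is to d; it is not evidence of what d is.

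**Step 4. Whether the placebo arm repairs this.** If both arms have the same d, with true proportions p₁ (active) and p₀ (placebo), the recorded difference is d × (p₁ − p₀). Blinding with equal ascertainment avoids favouring one arm, but incidence in each arm and the difference between them both shrink by the factor d.

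**The case against.** The strongest reply is that capture does not depend on complaints. Section 7.3.1 has staff observe subjects for signs at least daily in residence, records what is noted on examination and allows photographs. A reader who sees only the open question might infer that the data will be a tally of complaints. That is not supported, because noticed signs are a second route. What remains is that this route is unstructured and does not name the injection site.

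The timing of examinations is also defensible. The first is at 24 h, but those at 24, 48 and 72 h all fall within the three days in which the protocol expects reactions to resolve. The gap lies in the kind of examination, not its date.

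Reporting is largely in place. A reaction recorded as an adverse event is graded under the DAIDS table (Protocol Appendix 1) and counted by preferred term and treatment (SAP 8.6.1). The weakness is detection.

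Three stronger inferences should be resisted:

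- **That the under-count differs by dose.** Protocol Table 4 volumes rise from 0.047 to 1.12 mL, a ratio of 1.12 / 0.047 = 23.8. But nothing shows that the symptomless share changes with volume, and larger reactions could be easier to notice.
- **That escalation decisions are compromised.** The rules in Section 3.7 turn on clinically relevant signs or symptoms that the investigator judges to warrant stopping, related serious events, Grade 3 or 4 events, and liver and renal values. No route is shown from an unnoticed symptomless reaction to a different decision.
- **That site reactions are the leading animal finding.** The protocol does not rank findings, and laboratory signs of inflammation also appear in 4 of the 6 studies. The nodules came from 28 days of daily dosing, whereas this is a single-dose study.

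**Conclusion.** The point holds as a gap in ascertainment. After dosing there are no full examinations and no scheduled site inspections, so a visible reaction without symptoms enters the data only if staff happen to see it. Such reactions can be missed; the documents do not show that they will be. The under-count is of unknown size, and the figures above rest entirely on assumed p and d.

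This does not invalidate the trial, and no listed endpoint goes unmeasured, since the primary endpoints include no local tolerability score. It is still more than missing detail, because the symptom-directed rule is explicit and leaves no point after dosing at which the site must be looked at. The change is worth making because local tolerability falls within the primary objective, the protocol expects these reactions, and staff are already with the subject at nine postdose timepoints.

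**What to change.** In Protocol Appendix 6, add a row for injection-site inspection in every subject regardless of symptoms. Include a predose look as baseline, then inspections at postdose timepoints that already have vital signs or an examination. Refer to it in Section 7.3. Blinded staff should do it, not the unblinded nurse who gives the injection under Section 5.4. Record a clear site as well as a reaction, so that absence of findings is itself an observation. Grade findings with the DAIDS table already adopted. The sponsor should set the exact timepoints and content.

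In SAP 8.6, add a summary of the incidence and maximum grade of local reactions by treatment. Without it, inspection data held apart from adverse events would be listed only, under SAP 8.6.5. State how inspection findings relate to adverse event records, so that one reaction is not counted twice.

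Cost: a brief look at existing timepoints, one eCRF page and one table. The downside is more Grade 1 local events, in placebo as well as active subjects.

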**Appendix 7: Protocol Amendment(s)– Summary of Changes**

**Protocol Amendment 2 (Protocol Version 3)**

**PURPOSE:** To update wording related to the appearance and blinding requirements of CPT31 and placebo solutions.

**MODIFICATIONS TO PROTOCOL:**

**General Revisions:**

Section 3.5: Wording revised as no systemic exposure specifically defined in section 3.7

Section 5.2: Correction/clarification of timings

Section 5.4: Updates to appearance of CPT31 and placebo solution information and potential for required study blinding actions/processes.

**ADDITIONAL RISK TO THE SUBJECT:** There are no additional risks to the subjects.

---

**Protocol Amendment 3 (Protocol Version 4)**

**PURPOSE:** To update urine PK assessment to males only.

**MODIFICATIONS TO PROTOCOL:**

**General Revisions:**

Section 7 and 7.1.1: Wording updated to state urine samples for males only (for CPT-31 assay)

Appendix 6: Urine sampling information for PK updated to detail males only.

**ADDITIONAL RISK TO THE SUBJECT:** There are no additional risks to the subjects.

Abbreviations pertain to the statistical analysis plan (SAP) only (not the tables, figures, and listings [TFLs]).

ADaM	analysis data model
%AUC _{extrap}	percentage of AUC due to extrapolation from the last quantifiable concentration to infinity
AE	adverse event
A _e	amount of drug excreted in the urine at each collection interval and cumulative amount of drug excreted in the urine at each collection interval
ANOVA	analysis of variance
AUC _{0-∞}	area under the curve from time 0 to infinity
AUC _{0-t_{last}}	area under the curve from time 0 to the time of the last measurable concentration
BLQ	below the limit of quantification
CDISC	Clinical Data Interchange Standards Consortium
CI	confidence interval
CL/F	apparent total plasma clearance
CL _R	renal clearance
C _{max}	maximum concentration
CSR	clinical study report
CTCAE	Common Terminology Criteria for Adverse Events
CV	coefficient of variation
ECG	Electrocardiogram
F _e	percentage excreted in urine at each collection interval and cumulative percentage excreted in urine at each collection interval
GLSM	geometric least squares mean
ICH	International Council for/Conference on Harmonisation of Technical Requirements for Registration of Pharmaceuticals for Human Use
LLOQ	lower limit of quantification
Ln	natural log
LSM	least squares mean
MedDRA	Medical Dictionary for Regulatory Activities
PK	pharmacokinetic(s)
QTc	QT interval corrected for heart rate
QTcB	QT interval corrected for heart rate using Bazett's formula
QTcF	QT interval corrected for heart rate using Fridericia's formula
SAP	statistical analysis plan

SD	standard deviation
$t_{1/2}$	apparent terminal elimination half-life
TEAE	treatment-emergent adverse event
TFL	table, figure, and listing
T_{last}	time of the last quantifiable plasma concentration
T_{max}	time to maximum concentration
V_z/F	Apparent volume of distribution during the terminal elimination phase
WHODrug	World Health Organization Drug Dictionary

1. INTRODUCTION

This SAP has been developed after review of the clinical study protocol (Final Version 4.0 dated 27 July 2020) and electronic case report form.

This SAP describes the planned analysis of the pharmacokinetic (PK) and safety and tolerability data from this study. A detailed description of the planned TFLs to be presented in the clinical study report (CSR) is provided in the accompanying TFL shells document.

In general, the analyses are based on information from the protocol, unless they have been modified by agreement with Navigen Inc. A limited amount of information about this study (eg, objectives, study design) is given to help the reader's interpretation. This SAP must be finalized prior to the lock of the clinical database for this study. When the SAP and TFL shells are approved, they will serve as the template for this study's CSR.

This SAP supersedes any statistical considerations identified in the protocol; where considerations are substantially different, they will be so identified. If additional analyses are required to supplement the planned analyses described in this SAP, they may be performed and will be identified accordingly in the CSR. Any substantial deviations from this SAP will be agreed with Navigen Inc. and identified in the CSR.

This SAP is written with consideration of the recommendations outlined in the International Conference on Harmonisation (ICH) E9 guideline *Statistical Principles for Clinical Trials* and ICH E3 guideline *Structure and Content of Clinical Study Reports*.^{1,2}

The document history is presented in [Appendix 1](#).

2. STUDY OBJECTIVES

The primary objective of the study is:

- to assess the safety and tolerability of a single SC dose of CPT31 in healthy subjects

The secondary objectives of the study are:

- to characterize the single SC dose PK of CPT31
- to identify and characterize antibodies to CPT31

3. STUDY ENDPOINTS

3.1. Primary Endpoints

The primary safety endpoints for this study are as follows:

- incidence and severity of adverse events (AEs)
- incidence of laboratory abnormalities, based on hematology, clinical chemistry, and urinalysis test results

- 12-lead electrocardiogram (ECG) parameters
- vital signs measurements
- physical examinations
- anti-CPT31 antibodies, e.g., immunoglobulin (Ig)G, IgM

3.2. Secondary Endpoints

The single ascending dose PK outcome endpoints of CPT31 are as follows:

- AUC from time zero to infinity ($AUC_{0-\infty}$)
- AUC from time zero to the time of the last quantifiable concentration ($AUC_{0-t_{last}}$)
- C_{max}
- time of the maximum observed plasma concentration (T_{max})
- $t_{1/2}$
- apparent total plasma clearance (CL/F)
- apparent volume of distribution (V_z/F)
- renal clearance (CL_R)
- amount of drug excreted in the urine (A_e)
- percentage of dose excreted unchanged in the urine (F_e)

Other PK parameters may also be reported.

4. STUDY DESIGN

This study will comprise a placebo-controlled, double-blind, single-dose, sequential-group design. Overall, it is planned for 32 healthy subjects to be studied in 4 groups (Groups A1 to A4), with each group consisting of 8 subjects. In each group, 6 subjects will be randomized to receive SC CPT31 and 2 subjects will be randomized to receive matching placebo.

All groups will be divided into 2 cohorts, with each cohort being dosed 72 hours apart. The first (sentinel) cohort will comprise 2 subjects, with 1 subject receiving CPT31 and 1 subject receiving placebo. The second cohort will comprise 6 subjects, with 5 subjects receiving CPT31 and 1 subject receiving placebo. Potential subjects will be screened to assess their eligibility to enter the study within 28 days prior to the first dose administration.

Each subject will participate in 1 treatment period only. Subjects will reside at the Clinical Research Unit (CRU) from Day -1 (the day before dosing) to Day 6. All subjects will return

for a Follow-up visit 28 to 30 days after dosing.

[figure not shown]
Based on the ongoing review of the safety, tolerability, and PK results, additional nonresidential visits may be required. The number of additional visits per subject will not exceed 3 and will not extend beyond 30 days after dose administration.

The maximum total duration of study participation for each subject (from Screening through Follow-up visit) is anticipated to be approximately 8 weeks.

Dose escalation will occur a minimum of 7 days after all subjects complete all Day 6 assessments in the previous dose group.

[figure not shown]
An overview of the study design is shown in [Figure 1](#) and the planned dose levels are shown in [Figure 2](#).

Figure 1: Study Schematic

Abbreviations: CRU = Clinical Research Unit, N = number of subjects.

Figure 2: Planned Dose Levels

Abbreviations: N = number of subjects; SC = subcutaneous.

